### **6.6.1.2 Within participant dose modification in Part A**

For participants who experience dose-limiting toxicity, dose adjustments are permitted if it is considered in the best interest of the participant to continue therapy at the discretion of the investigator, in consultation with the Sponsor.

Participants who fail to receive the second planned dose of UCB6114 within 7 days of the scheduled administration day, during the DLT Observation Period, for reasons not related to toxicity will be replaced by a new participant in that cohort. The replaced participant may still continue participation in the study. Safety data for replaced participants will be included in all summary data and any DLTs experienced by the replaced participant will contribute to determination of MTD (Part A) or suitability of the dosing schedule (Part A1).

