#### 6.6.3.2 UCB6114 dose modifications

Study participants who experience Grade 4 (life-threatening) nonhematologic toxicity, including diarrhea and mucositis, which is at least possibly related to UCB6114, will be discontinued from treatment.

Treatment with UCB6114 may temporarily be suspended for up to 3 weeks beyond the scheduled treatment day until toxicities are resolved to CTCAE Grade 2 or less. If UCB6114 is

held for more than 3 weeks beyond the scheduled treatment day, then the participant will be discontinued from treatment and will be followed up for safety and efficacy per the Schedule of Activities.

For permitted adjustments of the infusion rate in case of AEs, refer to the IMP Handling Manual. Participants who experience severe or life-threatening infusion-related events (Grade 3 or 4) will not receive further infusions. Hypersensitivity/infusion-related events should be managed per institutional guidelines. Premedication with steroids may be administered at the discretion of the investigator.

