**Table 6-14: Dose modification for hematological toxicity**

Prior to Dosing (Day 1 or Day 15)	Toxicity		Dose level for subsequent cycles	
	CTCAE (V5.0) Toxicity Grade	ANC (x10  /L)	Oxaliplatin	5-Fluorouracil
If ANC <1.2 on Day 1 or Day 15, hold treatment and perform weekly blood counts.	1	≥1.2	Maintain dose level	Maintain dose level
	2	1.0 to <1.2	Maintain dose level	Maintain dose level
	3	0.5 to <1.0	Reduce 1 dose level	Maintain dose level

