## DLT Evaluatable Set

The DLT Evaluatable Set (DES) will include all study participants who, during the DLT assessment period:

- Receive the planned dose of UCB6114 (Part A and Part A1)
- Receive the planned dose of UCB6114 and at least 80% of the planned dose of TFD/TPI (Part B)
- Receive the planned dose of UCB6114 and at least 80% of the planned dose of mFOLFOX6 (Part C)
- Stopped treatment because of a DLT (any part of the study)

The DES will be used by the SMC for all dose escalation/de-escalation decision making.

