## 10.3 Planned safety and other analyses

### 10.3.1 Safety analyses

Safety will be assessed by clinical review of all relevant parameters including AEs, SAEs, laboratory values, vital signs, echocardiograms, ECG results and physical examination. Eastern Cooperative Oncology Group performance status will also be assessed from a safety perspective. Unless specified otherwise, the safety analyses will be conducted for the SS defined in Section 10.1. The results of these analyses will be presented by study part. For the dose escalation modules of the study (Part A, B, and C) tabulations will be provided by dose level and overall. For the dose optimization module of the study (Part A1) tabulations will be provided by cohort and overall. For the expansion modules (Parts D, E, F, and G), tabulations will be

provided by tumor type and overall. Some safety analyses may be performed based on the dose escalation, optimization, and expansion modules combined.

Summary tables and listings will be provided for all reported TEAEs, defined as AEs that start on or after the first administration of study treatment up until the SFU visit. A pre-treatment AE which increases in severity on or after the first dose of study treatment will also be counted as a TEAE. The reported AE term will be assigned a standardized preferred term using the current version of the Medical Dictionary for Regulatory Activities (MedDRA).

The causal relationship between the occurrence of an AE and study medication will be judged by the investigator. In the event that a participant experiences repeat episodes of the same AE, then the event with the highest CTCAE severity grade and strongest causal relationship to study medication will be used for purposes of incidence tabulations.

An overview of the number and percentage of participants who experience TEAEs will be presented. This summary will include the number and percentage of participants with any TEAEs, serious TEAEs, related TEAEs (related to UCB6114, TFD/TPI [Part B], any individual component of mFOLFOX6 [Part C], or more than 1 of the treatments [Part B and Part C]), discontinuation due to TEAEs, CTCAE Grade 3 or 4 TEAEs, DLTs, AEs leading to death, and TEAEs leading to death; event counts will also be included against each of these categories.

In addition, the following summaries will be presented by MedDRA System Organ Class, High Level Term and Preferred Term:

- Incidence of all TEAEs, serious TEAEs, and non-serious TEAEs

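### The DLT Evaluable Set has no criterion for having experienced a DLT, so some Cycle 1 DLTs fall outside the set that drives escalation, in conflict with other sections

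*Protocol*

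**What the plan says.** Section 10.1 of the protocol gives two ways into the DES during the DLT assessment period. The first is exposure. For monotherapy the criterion is "Receive the planned dose of UCB6114 (Part A and Part A1"; for the mFOLFOX6 combination it is "Receive the planned dose of UCB6114 and at least 80% of the planned dose of mFOLFOX6 (Part C", and Part B has the same form with TFD/TPI. The second is "Stopped treatment because of a DLT (any part of the study". The section then adds: "The DES will be used by the SMC for all dose escalation/de-escalation decision making".

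Elsewhere the protocol allows treatment to continue after toxicity:
- Section 6.6.1.2 permits dose adjustment after a DLT in Part A.
- Section 6.6.3.2 says "Treatment with UCB6114 may temporarily be suspended for up to 3 weeks beyond the scheduled treatment day"; Sections 6.6.2.2 and 7.1.4 say the same.
- Section 6.6.2.3 allows TFD/TPI to be interrupted and resumed.
- Table 6-14 says, for mFOLFOX6, "If ANC <1.2 on Day 1 or Day 15, hold treatment and perform weekly blood counts", with resumption possible within 2 weeks.

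Other sections count DLTs with no exposure condition. Section 6.6.1.2 says of participants replaced after missing the second dose for non-toxicity reasons that "any DLTs experienced by the replaced participant will contribute to determination of MTD (Part A) or suitability of the dosing schedule (Part A1".

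**The concern.** A DLT can itself be the reason why the planned Cycle 1 dose is not reached. An evaluability rule based on exposure therefore needs an explicit exception for anyone who has had a DLT. Here the exception covers only treatment stopped because of the DLT. A DLT followed by a hold, a reduced dose, or a missed dose or withdrawal for an unrelated reason is left out on the natural reading.

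The count at stake feeds the rolling-6 rule in Part A, the limit of 3 DLT participants per cohort in Part A1 and the mTPI tables in Parts B and C. Those rules work on cohorts of 3 to 9, so one uncounted case can change the recommendation.

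**Working it through.** **1. DLT courses that fit neither route.** The DLT window is Days 1 to 28 of Cycle 1.
- UCB6114 Day 15 dose held for the full 3 weeks: 15 + 21 = Day 36, outside the window.
- TFD/TPI not taken on Days 8 to 12: 5 of 10 dosing days = 50%, below 80%.
- mFOLFOX6 held on Day 15 for the full 2 weeks: 15 + 14 = Day 29, so 1 of 2 administrations = 50%.
- Part A, Day 15 dose adjusted after a DLT: not the planned dose, and treatment has not stopped.
- DLT, then second dose missed or consent withdrawn for an unrelated reason: planned dose not received, and treatment not stopped because of the DLT.

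**2. Sections that point the other way.**
- 4.1.2.2 (Part A): DLTs over the whole of Cycle 1 are used.
- 4.1.3 (Part A1): the limit is 3 or more participants with DLTs, with no reference to the DES.
- 4.1.4.2.2 and 4.1.5.2.2 (Parts B and C): the algorithm uses everyone treated at the dose level, and the columns of Tables 4-2 and 4-3 are numbers treated.
- 6.6.1.2: DLTs in replaced participants count (Parts A and A1 only).
- 10.6: a participant discontinued from the study early remains evaluable if a DLT came before withdrawal, whatever the reason for withdrawal.

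**3. Reproducing Table 4-2 (Table 4-3 is identical).** Inputs from the protocol: target 25%, equivalence interval 20% to 30%. Assumed, because the protocol does not state them: a Beta(1,1) prior, and DR when P(rate > 0.25) exceeds 0.95. Each decision takes the interval with the largest posterior probability per unit length.
- 0/3, posterior Beta(1,4): below 0.20, (1 − 0.8⁴)/0.2 = 0.5904/0.2 = 2.95; 0.20 to 0.30, (0.4096 − 0.2401)/0.1 = 1.70; above 0.30, 0.2401/0.7 = 0.34. Escalate.
- 1/3, posterior Beta(2,3): 0.1808/0.2 = 0.90; (0.3483 − 0.1808)/0.1 = 1.68; 0.6517/0.7 = 0.93. Stay.

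All 43 filled cells match.

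**4. Effect of losing one DLT case.**

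| True count | Decision | Lost case replaced by a DLT-free participant | Lost case not replaced |
|---|---|---|---|
| 1/3 | Stay | 0/3 Escalate | 0/2, no table entry |
| 2/3 | De-escalate | 1/3 Stay | 1/2, no table entry |
| 1/6 | Stay | 0/6 Escalate | 0/5 Escalate |
| 3/6 | De-escalate | 2/6 Stay | 2/5 Stay |
| 2/9 | Stay | 1/9 Escalate | 1/8 Escalate |
| 4/9 | De-escalate | 3/9 Stay | 3/8 Stay |

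Some cells do not change (2/6 and 1/6 are both Stay), but where the decision changes it moves toward the higher dose or a weaker de-escalation signal.

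**5. Size as a probability.** Let p be the true DLT rate and f the share of DLT cases lost and replaced. The rate among counted participants is q = p(1 − f)/(1 − pf), and P(escalate after the first 3 evaluable) = (1 − q)³. For p = 0.40 and f = 0.10: q = 0.36/0.96 = 0.375 and 0.625³ = 24.4%.

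| p | f = 0 | f = 10% | f = 25% | f = 50% |
|---|---|---|---|---|
| 25% | 42.2% | 45.5% | 51.2% | 63.0% |
| 33% | 30.1% | 33.3% | 38.9% | 51.7% |
| 40% | 21.6% | 24.4% | 29.6% | 42.2% |

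For Part A at p = 33%, the binomial probability of at most 1 DLT in 6 is 35.8%, 40.5%, 48.8% and 66.1% for the same four values of f.

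**The case against.** Several points on the other side stand and limit the finding.

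- A reader might infer that most DLTs would be lost. The documents do not support that. Section 7.1.3 makes discontinuation the default for unacceptable toxicity. Sections 6.6.2.2 and 6.6.3.2 discontinue treatment for Grade 4 nonhematologic toxicity at least possibly related to UCB6114 and end infusions after Grade 3 or 4 infusion-related events. Those participants enter through the stopped-treatment bullet. DLTs after the Day 15 dose generally stay in, and Part A1 Cohorts 3 and 4 have only one Cycle 1 dose.
- The 50% figure for mFOLFOX6 applies only if nothing more is given by Day 28. If treatment resumes on Day 22 at the Table 6-14 level for Grade 4 neutropenia, oxaliplatin reaches (85 + 65)/170 = 88% and 5-fluorouracil (2800 + 2000)/5600 = 86%, both above 80%.
- Sections 7.4 and 9.2.9 use the word stop for pauses, so a hold could be read as a stop. That reading brings in the held cases. It does not bring in an adjusted dose given without a pause, or a DLT followed by a missed dose or withdrawal for another reason.
- A lost case turns 1/3 into 0/3 only if a DLT-free participant takes the place. Mandatory replacement for a missed second dose (7.1.4) is limited to non-toxicity reasons, and 10.6 otherwise only permits replacement. However, Sections 4.1.4 and 4.1.5 require at least 3 evaluable participants per dose level, and at 6 or 9 treated the listed changes occur without replacement.
- The SMC adjudicates DLTs and weighs all safety data, and the mTPI table only informs its decision. The event would be seen. The written counting rule would still exclude it.

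**Conclusion.** The DES definition is wrong as written and conflicts with the sections listed above. The exposure is limited to DLTs where the dose threshold is missed within the window and treatment was not stopped because of the DLT. Where that happens, the decision changes shown favour escalation.

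The one-case changes follow directly from Tables 4-2 and 4-3. The probabilities are illustrations. They assume a true DLT rate, binomial counts and replacement of lost cases, and the share f appears nowhere in the documents. At p = 40% the effect runs from 2.8 percentage points (24.4 − 21.6) at f = 10% to 20.6 points (42.2 − 21.6) at f = 50%.

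A reader might also infer that the primary endpoint, incidence of DLTs, is biased. The documents do not support this. Section 10.3.1 says "Unless specified otherwise, the safety analyses will be conducted for the SS defined in Section 10.1", and that set keeps every treated participant with a DLT. The denominator for the reported rate can be left to the SAP. The defect is in the decision set only.

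**What to change.** Replace the fourth DES bullet with: *or experience a DLT during the DLT assessment period, regardless of the amount of study treatment received or whether treatment was held, modified, resumed or stopped.* Such a participant then counts in both the numerator and the denominator.

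Reconcile Sections 4.1.2.2, 4.1.3, 4.1.4.2.2, 4.1.5.2.2, 6.6.1.2, 7.1.4 and 10.6 with that wording. In particular, the statement that DLTs in replaced participants count should cover Parts B and C as well as Parts A and A1, and the DLT exception in 10.6 should not be confined to participants discontinued from the study.

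The cost is one bullet and a few aligning sentences in an amendment, with matching wording in the SMC charter. No dosing, hold or discontinuation rule changes, and the planned sample size is unaffected.

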## 10.2 General statistical considerations

All analyses will be performed using SAS® Version 9.2 or higher (SAS Institute, Cary, NC, US).

Descriptive statistics will be used to provide an overview of the Baseline, safety, PK, PD, and other exploratory results. For categorical and ordinal variables, the number and percentage of participants in each category will be presented. The denominator for the percentages will be based on the number of participants appropriate for the purpose of analysis. Unless otherwise noted, all percentages will be expressed to 1 decimal place. For continuous variables, descriptive statistics will include, but will not be limited to, the number of participants, mean, median, standard deviation, minimum, and maximum.

Definitions of Baseline for each variable, as applicable, will be included in the SAPs for each module.

No formal hypothesis testing will be performed in Part A, Part A1, Part B or Part C.

## 10.3 Planned safety and other analyses

### 10.3.1 Safety analyses

Safety will be assessed by clinical review of all relevant parameters including AEs, SAEs, laboratory values, vital signs, echocardiograms, ECG results and physical examination. Eastern Cooperative Oncology Group performance status will also be assessed from a safety perspective. Unless specified otherwise, the safety analyses will be conducted for the SS defined in Section 10.1. The results of these analyses will be presented by study part. For the dose escalation modules of the study (Part A, B, and C) tabulations will be provided by dose level and overall. For the dose optimization module of the study (Part A1) tabulations will be provided by cohort and overall. For the expansion modules (Parts D, E, F, and G), tabulations will be

provided by tumor type and overall. Some safety analyses may be performed based on the dose escalation, optimization, and expansion modules combined.

Summary tables and listings will be provided for all reported TEAEs, defined as AEs that start on or after the first administration of study treatment up until the SFU visit. A pre-treatment AE which increases in severity on or after the first dose of study treatment will also be counted as a TEAE. The reported AE term will be assigned a standardized preferred term using the current version of the Medical Dictionary for Regulatory Activities (MedDRA).

The causal relationship between the occurrence of an AE and study medication will be judged by the investigator. In the event that a participant experiences repeat episodes of the same AE, then the event with the highest CTCAE severity grade and strongest causal relationship to study medication will be used for purposes of incidence tabulations.

An overview of the number and percentage of participants who experience TEAEs will be presented. This summary will include the number and percentage of participants with any TEAEs, serious TEAEs, related TEAEs (related to UCB6114, TFD/TPI [Part B], any individual component of mFOLFOX6 [Part C], or more than 1 of the treatments [Part B and Part C]), discontinuation due to TEAEs, CTCAE Grade 3 or 4 TEAEs, DLTs, AEs leading to death, and TEAEs leading to death; event counts will also be included against each of these categories.

In addition, the following summaries will be presented by MedDRA System Organ Class, High Level Term and Preferred Term:

- Incidence of all TEAEs, serious TEAEs, and non-serious TEAEs
- Incidence of TEAEs by maximum relationship and maximum CTCAE severity grade
- Incidence of TEAEs leading to a temporary interruption and/or reduction in study treatment
- Incidence of TEAEs leading to discontinuation of study treatment
- Incidence of fatal TEAEs by relationship
- Incidence of adverse events of special interest (AESIs) (Hy's Law – see Section 9.2.6)
- Incidence of infusion-related (hypersensitivity) reactions

For the dose escalation and optimization modules, the observed DLT rate in each dose cohort will be calculated by the crude proportion of participants who experience DLT. Multiple concurrent AEs leading to DLT will be considered a single DLT.

Deaths that occur on study (defined as during treatment or within 30 days of treatment discontinuation) will be reported in a participant listing, which will include the primary cause of death and the number of days between the date of the final dose of study medication and death.

Observed values and changes from Baseline in clinical chemistry, hematology, urinalysis, and coagulation parameters will be summarized at each visit. In addition, for each of these parameters, the Baseline value, the minimum, maximum, average, and last post-Baseline value for each participant will be summarized by cycle using descriptive statistics. These post-Baseline summary measures will be calculated based on laboratory assessments performed at the scheduled time points common to all cycles of study treatment.

Laboratory values will be assigned severity grades when available using the NCI CTCAE criteria. Directional shifts in laboratory toxicity grades (comparing Baseline grade with worst post-Baseline grade) will be analyzed using standard shift tables, presenting the number and proportion of participants and their maximum grade shift. For analytes without a CTCAE severity grade assigned, the shift table will present directional shifts from Baseline to above or below the laboratory standard normal range using the maximum increase and/or decrease observed throughout the course of treatment/observation.

In addition, serial vital signs measurements will be obtained during participant's UCB6114 treatment and postdose (per the Schedules of Activities for Part A [[Table 1-4](#)], Part A1 [[Table 1-5](#) and [Table 1-6](#)], Part B [[Table 1-7](#)], and Part C [[Table 1-8](#)]). On the first day of each participant's UCB6114 treatment, vital signs will be taken in conjunction with serial PK sampling. For each participant, the vital signs change from the predose value will be summarized in a descriptive manner.

In Part A, vital signs will be measured at multiple time points on treatment days (predose, 10min and 30min after the start of the infusion, at the end of infusion, and at 1 hour after the end of the infusion). In addition, on Cycle 1 Day 1, vital signs will also be assessed at 2 hours and 8 hours after the end of the infusion. On non-dosing visits, vital signs will be measured prior to PK sampling.

In Part A1, vital signs will be measured at multiple time points on treatment day (predose, 10 minutes and 30 minutes after the start of the infusion, at the end of the infusion and 2 hours after the end of the infusion. In addition, on Cycle 1 Day 1, vital signs will also be assessed at 5 hours after the end of the infusion.

In Part B and Part C, on Day 1 of Cycle 1, vital signs will be measured at multiple time points (per the Schedules of Activities for Part B [[Table 1-7](#)], and Part C [[Table 1-8](#)]). At all other scheduled visits (Day 8, 15, and 22 of Cycle 1 and Days 1 and 15 of all subsequent cycles of study treatment), vital signs will be measured prior to UCB6114 dosing on treatment days.

Observed vital sign measurements and changes from Baseline will be summarized by visit and timepoint using descriptive statistics. In addition, for each of the vital signs, the Baseline value, the minimum, maximum, average and last post-Baseline value for each participant will be summarized by cycle using descriptive statistics. These post-Baseline summary measures will be calculated based on vital sign measurements performed at the scheduled time points common to all cycles of study treatment.

For the multiple vital sign measurements on Day 1 of Cycle 1, changes from the predose value will be calculated at each postdose time point and summarized using descriptive statistics.

In Part A, on Days 1 and 15 of Cycle 1, ECGs will be performed at multiple time points relative to the dose of study treatment (predose, end of infusion, and 8 hours post end of infusion prior to PK sampling). At all other dosing visits (Days 1 and 15 of all subsequent cycles of study treatment), ECGs will be performed predose. On non-dosing visits, ECGs will be performed prior to PK sampling.

In Part A1, ECGs will be performed at Screening; during Cycle 1 prior to dosing, at the end of the infusion, and 2 hours after the end of infusion; during each subsequent cycle prior to dosing with UCB6114 on Day 1.

In Part B and Part C, on Days 1 and 15 of Cycle 1, ECGs will be performed at multiple time points relative to dosing with UCB6114 (predose, end of infusion, and 2 hours post end of infusion prior to PK sampling). At all other UCB6114 dosing visits, ECGs will be performed prior to dosing with any study medication and as per Schedule of Activities.

Observed values and changes from Baseline for these ECG parameters will be listed and summarized by visit using descriptive statistics. The mean of the triplicate measurements taken for each parameter will be used in the summary. In addition, for each of the ECG parameters, the Baseline value, the minimum, maximum, average and last post-Baseline value for each participant will be summarized by cycle using descriptive statistics. These post-Baseline summary measures will be calculated based on ECG measurements performed at the scheduled time points common to all cycles of study treatment.

All summaries and listings of ECG data will be based on the local (site) 12-lead ECG measurements.

Electrocardiograms will also be collected for central reading, the data from which will be analyzed and reported separately.

Physical examination data will be listed only.

Prior and concomitant medications will be coded to the generic term using the current version of the World Health Organization Drug Dictionary and will be tabulated by cohort and listed by participant.

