m Tumor assessments including spiral CT or MRI scan of the chest, abdomen, and any other area of known or suspected disease, must be obtained at Screening. A CT or MRI scan that is dated prior to consent (up to 42 days prior to starting IMP) for this study may be used as the Screening assessment, where this has been performed as per standard of care or at the end of a prior study. The same method of assessment is to be used per participant for the duration of study participation. Tumor assessments are to be performed every 8 weeks from Day 1 ( $\pm$  7 days). Tumor assessment at SFU is not required if the participant has withdrawn due to progressive disease or if the previous tumor assessment was within 42 days of SFU visit.

n Follow-up of AEs: AEs will be recorded up to 30 days after the last dose of study medication. After that time, any unresolved drug-related AEs should be followed until resolution or stabilization of the AE to obtain the date of resolution/stabilization (this follow-up can be via routine clinic visits or correspondence with a treating physician or other healthcare professional).

o Blood samples for circulating gremlin-1 analysis will be collected at Cycle 1 Day 1, pre-dose (within 30 min prior to dosing), end of infusion (+15min), and 4h (+1h) post-infusion as well as at Day 15 at predose (within 30min prior to dosing) or on day of visit if a non-dosing day. At all subsequent cycles, blood samples will be collected at Day 1 predose (within 30min prior to dosing) and at the SFU Visit; for Cycle 3 only, an additional 4h (+1h) postdose sample should be taken on Day 1. An additional sample should also be collected on the day of on-treatment biopsy (only if taking place on a day where no PK samples are scheduled).

p To be confirmed based on Part A Cohorts 1 to 3 analysis.

q Baseline biopsy should be collected between Day -28 and Day -1. Whenever possible, on-treatment biopsy should be performed within 2 weeks post Cycle 1 Day 15 (ie, between Cycle 1 Day 15 and Cycle 2 Day 1). If on-treatment biopsy occurs a non-dosing day, an additional PK and an additional cGremlin-1 samples should be collected on the day of biopsy.

r If an historical tumor biopsy specimen obtained prior to the participant's entry into the study (eg, at the time of diagnosis) is available, samples of this tissue will be requested for PD analysis at the time of consent.

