#### **4.1.3 Part A1 – Dose optimization (alternative dosing schedules)**

Part A1 is a multicenter, non-randomized, open-label, dose optimization module of Study ONC001 to evaluate alternative dosing schedules and infusion times for UCB6114 administered as monotherapy in patients with unresectable locally advanced or metastatic colorectal cancer, gastric cancer, cancer of the gastro-esophageal junction, or pancreatic cancer.

Part A1 may commence after the fifth cohort in Part A (Cohort 5) is considered sufficiently █ by the SMC (DLT rate less than 33%). The planned dose optimization scheme for Part A1 will assess the safety and tolerability of the drug new formulation and will explore shortening of the infusion time and less frequent dosing as follows:

- Cohort 1: 2000mg Q2W (60-minute iv infusion), 28-day treatment cycle
- Cohort 2: 2000mg Q2W (30-minute iv infusion), 28-day treatment cycle
- Cohort 3: 3000mg Q3W (90-minute iv infusion), 21-day treatment cycle
- Cohort 4: 4000mg Q4W (120-minute iv infusion), 28-day treatment cycle

Details of each planned cohort are provided in [Table 6-6](#).

Up to 32 participants will be allocated 1:1:1:1 to one of the 4 cohorts, with each cohort enrolling 8 study participants including 1 sentinel participant with an observation period of 48 hours.

The enrollment of a sentinel participant in each cohort has been included as an additional risk mitigation measure to monitor infusion related reactions and other early onset treatment-related AEs. Each sentinel participant will be assessed for at least 48 hours following the first administration of UCB6114 in the first cycle and the SMC will convene before further participants within the cohort can be enrolled.

The SMC will also convene after 25%, 50% and 100% of study participants in Part A1 have completed the required 28-day observation period. If deemed necessary, an additional SMC meeting can convene after 75% of the participants have completed the required observation period. If 1 DLT, or more, (refer to Section 4.1.2.4 for the definition of DLTs) are reported for a cohort then, an ad-hoc SMC will convene to determine if the dosing schedule and study can continue as planned.

If 3 or more participants experience DLT(s) in a given cohort, no further participants will be enrolled in the cohort and the dosing schedule will be considered to be unacceptably toxic.

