After consultation, the SMC will provide recommendations which could include to expand enrollment in a particular cohort to gain additional safety data, continue this Part with modifications or temporary suspension of enrollment in a particular cohort. Details are described in a SMC Charter.

The planned duration of treatment is 2 cycles. Participants may, however, remain in the study for additional cycles if they are receiving therapeutic benefit (SD, PR, or CR) or until they fulfill one of the criteria for treatment discontinuation. Participants will continue treatment until disease progression, unmanageable toxicity, or withdrawal from the study. Upon discontinuation from treatment, participant will be referred to appropriate follow-up care per the Investigator's judgment.

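### Part A1 reports TEAEs by cohort as crude percentages over a window whose length depends on the dosing schedule, modestly understating incidence in the Q4W cohort against the Q2W reference

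*Protocol*

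**What the plan says.** Protocol Table 3-1 makes incidence and severity of TEAEs primary endpoints for Part A1. Section 10.3.1 fixes how they are shown. The layout is given as "For the dose optimization module of the study (Part A1) tabulations will be provided by cohort and overall", the measure is the number and percentage of participants with event counts added, and TEAEs are "defined as AEs that start on or after the first administration of study treatment up until the SFU visit". Footnote n of Table 1-5 limits the recording period: "AEs will be recorded up to 30 days after the last dose of study medication". Footnote m of Table 1-6 says the same for Cohort 3.

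Section 4.1.3 sets the schedules:

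- "Cohort 1: 2000mg Q2W (60-minute iv infusion), 28-day treatment cycle" (Cohort 2 has the same interval and cycle length, with a shorter infusion)
- "Cohort 3: 3000mg Q3W (90-minute iv infusion), 21-day treatment cycle"
- "Cohort 4: 4000mg Q4W (120-minute iv infusion), 28-day treatment cycle"

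On duration, the same section says "The planned duration of treatment is 2 cycles". It then allows participants who benefit to go on, and adds: "Participants will continue treatment until disease progression, unmanageable toxicity, or withdrawal from the study". Each cohort has 8 participants. Table 6-6 labels Cohort 1 the reference. Section 10.3.1 names no common window and no rate per unit of observation time for TEAEs.

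**The concern.** A crude percentage depends on how long each participant is watched. Here the end of the watching period is tied to the last dose, and the date of the last dose depends on the interval between doses, which is what Cohorts 3 and 4 are testing. Two schedules with identical toxicity over time can therefore show different crude TEAE percentages.

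Part A1 exists to judge alternative schedules, with Cohort 1 as the named reference and no formal test. The by-cohort table is what readers will look at. If the difference in observation time runs in one direction, a less frequent schedule gains a small apparent advantage on a primary endpoint.

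**Working it through.** **Inputs.** Schedules, cycle lengths, the two-cycle plan and 8 participants per cohort come from Section 4.1.3. The 30-day tail comes from Tables 1-5 and 1-6, as does the first scan at 8 weeks from Day 1 (about Day 57, ±7 days). The protocol states no window length, so it has no figure to reproduce. The documents give no TEAE rate, so incidence is an assumption, varied below.

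**Step 1: exactly two cycles.** Window end = day of last scheduled dose + 30.

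- Cohorts 1 and 2: doses on Days 1, 15, 29, 43, so 43 + 30 = Day 73
- Cohort 4: doses on Days 1, 29, so 29 + 30 = Day 59
- Cohort 3: doses on Days 1, 22, so 22 + 30 = Day 52

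**Step 2: other stopping points.** Two cycles is not a cap, so the same rule is applied to other stopping dates.

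| Treatment stops | Cohorts 1/2 | Cohort 3 | Cohort 4 |
|---|---|---|---|
| After exactly two cycles | Day 73 | Day 52 | Day 59 |
| At a scan on Day 50 or 57, no dose that day | Day 73 | Day 73 | Day 59 |
| At a late scan on Day 64, Day 57 dose already given | Day 87 | Day 73 | Day 87 |
| After Day 84 | Day 101 | Day 94 | Day 87 |
| After Day 112 | Day 129 | Day 136 | Day 115 |
| After Day 168 | Day 185 | Day 178 | Day 171 |

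**Step 3: what is systematic.** Every Q4W dosing day (1, 29, 57, ...) is also a Q2W dosing day. For any common stopping date, Cohort 4's last dose therefore cannot fall later than that of Cohorts 1/2. It is 14 days earlier whenever stopping falls after the second Q2W dose of a 28-day cycle and before the next cycle's first dose. Stopping at the nominal 8-week scan meets that condition: 73 − 59 = 14 days, and likewise 101 − 87, 129 − 115 and 185 − 171. The gap closes when the scan is late and the next Day 1 dose has already been given.

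Cohort 3 has no such pattern against Cohorts 1/2. It is 21 days shorter for exactly two cycles, equal at the Day 57 scan, and 7 days longer after Day 112.

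**Step 4: size under an assumed constant, equal hazard and a two-cycle stop.** If p is the incidence over the 73-day window, a cohort with window w shows 1 − (1 − p)^(w/73).

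| Assumed p, Cohorts 1/2 | Cohort 4 (w = 59) | Cohort 3 (w = 52) |
|---|---|---|
| 20% | 16.5% | 14.7% |
| 50% | 42.9% | 39.0% |
| 70% | 62.2% | 57.6% |
| 90% | 84.4% | 80.6% |

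For p from 10% to 95%, the largest gap is about 7.8 points in Cohort 4 and 12.4 points in Cohort 3. In participants that is 8 × 0.078 = 0.6 and 8 × 0.124 = 1.0. For comparison, 4 of 8 has an exact 95% confidence interval of 15.7% to 84.3%.

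**The case against.** The strongest reply is that this is analysis-plan detail. Section 10 announces a statistical analysis plan for each module, and nothing in the protocol prevents an exposure-adjusted table there. The Part A1 analysis is descriptive, with no hypothesis test (Section 10.2). The rule for calling a schedule unacceptably toxic counts DLTs, not TEAE percentages, so no stated decision turns on this table. Cohort 1 is the reference because it repeats the Part A Cohort 5 schedule with the new formulation, and no TEAE contrast between cohorts is specified. The distortion is also small beside the imprecision of 8 participants.

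Much of that stands, and it limits the weight of the point. It does not remove it. Section 10.3.1 is not silent: it fixes the measure, the window and the by-cohort layout. Small numbers are no reason to keep a systematic difference that can be removed with data already collected.

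A reader might go further and infer that the protocol formally compares cohorts on these percentages, and that the less frequent schedules as a group look safer by construction. The documents do not support either. Treatment continues past two cycles in participants who benefit, so the Day 73, 59 and 52 figures describe one nominal case. Cohort 3's shortfall requires stopping before its Day 43 dose. That would precede the 8-week scan in Table 1-6. Section 9.6.1 times scans at Days 21 to 28 of even cycles, which does not fit 21-day cycles; those passages need reconciling.

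A reader might also extend the point to the by-cycle laboratory, vital-sign and ECG summaries. By-visit summaries stand beside these, with shift tables for the laboratory data, so that is minor.

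**Conclusion.** The point holds in a limited form. The crude TEAE measure in Part A1 is taken over a window that depends on the schedule being evaluated. For Cohort 4 against the Q2W cohorts, the difference in observation time for a common stopping date runs one way, and it is 14 days when treatment stops at the nominal 8-week scan. Cohort 4's crude incidence is therefore biased modestly downward. For Cohort 3 no general direction can be claimed.

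The maximum spurious gaps, about 8 points for Cohort 4 and 12 for Cohort 3, rest on a constant hazard equal across cohorts, a stop after exactly two cycles, and full 30-day follow-up. Events that cluster early, such as infusion reactions, would show little or no gap. This is an inexpensive improvement to the reporting of a primary endpoint. It does not undermine the design or its DLT rule.

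**What to change.** In Section 10.3.1, for Part A1, add two displays by cohort:

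1. Incidence of TEAEs, Grade 3 or higher TEAEs and serious TEAEs with onset on Days 1 to 28 from first dose. A participant given only the Day 1 dose is due to be followed to 1 + 30 = Day 31, so 30-day follow-up covers this window for everyone dosed, apart from death, withdrawal or an early Safety Follow-Up visit.
2. For the whole study, event rates per participant-time of AE observation, or a time-to-first-event estimate. The latter is safer if events cluster early, because a rate then looks high in whichever cohort is observed for less time.

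Read both beside the existing crude table, which stays. The common window equalises observation time, not the amount of drug received.

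The cost is wording and a few extra tables from data already collected, with no new visits and no change to treatment. The small downside is that events after Day 28 appear only in the whole-study and crude displays.
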